#### 6.4.1.4 Recording Adverse Events

AE reporting will extend from signing of informed consent until completion of Follow-up Visit. AEs occurring after the end of the study should be reported to the Sponsor by the Investigator if the Investigator considers there is a causal relationship with the study drug.

All AEs, regardless of the relationship to study drug, will be recorded in the eCRF.

All AE reports should contain a brief description of the event, date and time of onset, date and time of resolution, intensity, treatment required, relationship to study drug, action taken with the study drug, outcome, and whether the event is classified as serious.

#### *6.4.1.5 Reporting Serious Adverse Events*

All SAEs that occur during the period of observation, and all SAEs occurring up to 30 days after receiving the last dose of study drug, whether considered to be associated with the study drug or not, must be reported within 24 hours by telephone, fax, or eCRF to the PAREXEL Safety Contact using the numbers in the List of Study Personnel.

SAEs occurring after the end of the study should be reported to the Sponsor/PAREXEL by the Investigator if the Investigator considers there is a causal relationship with the study drug.

The minimum information required for an initial report is:

- Name of person sending the report (i.e., name, address of Investigator);
- Subject identification (screening/randomization number, initials, NOT subject name);
- Protocol number;
- Description of SAE;
- Causality assessment, if possible.

However, as far as possible all points on the SAE form should be covered in the initial report, or the completed SAE form itself must be faxed to the PAREXEL Safety Contact. The original SAE form must then be sent by mail to the PAREXEL Safety Contact. In addition, the event must be documented in the EDC system.

In case the PAREXEL Safety Contact cannot be contacted (e.g., out of normal working hours or at weekends), an automated reporting service is available. The required information should be faxed and a message should be left on the voicemail service (for phone/fax numbers see the numbers in the List of Study Personnel).

After receipt of the initial report, the safety center will review the information and, if necessary, contact the Investigator, to obtain further information for assessment of the event. PAREXEL will be responsible for all information processing and reporting according to local legal requirements. Where necessary, Investigators will inform Regulatory Authorities in their own countries.

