**Table 3-2: Dose Groups for Part B**

KM-819 Dose (mg)	Subjects on KM-819 (n)	Subjects on placebo (n)	Total Subjects in Group (n)	Age Group
30†	6	2	8	Young adult male subjects
100†	6	2	8	
200†	6	2	8	
400†	6	2	8	
200	6	2	8	Elderly male or post-menopausal female subjects

† Doses between the current planned range may be assigned depending on safety, tolerability, and pharmacokinetic data from previous subjects and cohorts.

All subjects will undergo a Screening period of up to 28 days and an 8-day Confinement period when they are hospitalized for study activities (Day -1 to Day 8). Subjects are required to return for a Follow-up Visit on Day 14. See Figure 3-2 for Part B MAD study design.

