## **6.4 Safety Variables**

### **6.4.1 *Adverse Events***

#### **6.4.1.1 *Collection of Adverse Events***

It is responsibility of the Investigator to collect all AEs (both serious and non-serious) derived by spontaneous, unsolicited reports of subjects, by observation and by routine open questionings e.g., "How have you felt since I last saw you?"

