## 7 STUDY CONDUCT

### 7.1 Schedule of Procedures

**Table 7-1: Schedule of Assessments for Part A (SAD)**

Assessments	Screening Period (V1)	Confinement Days (V2)				Outpatient Visit Day (V3-V4)		Follow-up Visit (V5)
	Day -28 to Day -2	-1	1 	2	3 	Day 4	Day 7	Day 14 (±1 day)
Informed Consent	X							
Randomization and Study Drug Administration 			X					
Inclusion/Exclusion Criteria	X	X 						
Demography	X							
Medical/Medication History	X							
Assessment of AEs	X	X	X	X	X	X	X	X
Concomitant Medications	X	X	X	X	X	X	X	X
Vital Signs 	X	X	X	X	X	X	X	X
12-lead ECG 	X	X	X	X			X	X
Physical Examination	X	X			X	X	X	X
Height, Weight, BMI 	X							
Serology 	X							
Drug/Alcohol/Cotinine Screen	X	X						
Safety laboratory: Hematology, Serum Chemistry, Urinalysis 	X	X		X			X	X
Blood Pharmacokinetic Sampling 			X	X	X	X		
Urine Sampling 				X	X			
Scales 			X	X	X	X		
C-SSRS 	X				X			

AE: adverse event; BMI: body mass index; BP: blood pressure; C-SSRS: Columbia Suicide Severity Rating Scale; K-WAIS-IV: Korean Wechsler Adult Intelligence Scale-IV; ECG: electrocardiogram;

ED: Early Discontinuation; HCV: hepatitis C virus; HBsAg: hepatitis B surface antigen; HAV: hepatitis A virus; HIV: human immunodeficiency virus; VAS: Visual Analogue Scale; POMS: Profile of Mood States

1. On Day 1, any predose procedures should be performed within 2 hour before study drug administration.
2. Discharge assessments to be performed for ED are the Day 3 assessments supplemented with an ECG and safety labs, see Section 7.2.4.
3. Randomization occurs on Day 1 prior to dosing.
4. Confirmation of inclusion and exclusion criteria.
5. Vital signs include tympanic temperature, supine pulse and supine BP. Vital signs will be collected after the subject has been in a supine position for at least 5 minutes. On Day 1, vital signs will be measured at predose, and at 0.5, 1, 2, and 4 hour postdose.
6. 12-lead ECGs will be obtained in triplicate within 5 minutes, with at least a 1-minute interval. On Day 1, ECGs will be recorded at predose and at 1 hour postdose. ECGs should be performed prior to pharmacokinetic and safety laboratory blood draws.
7. Screening height and weight will be used for BMI calculation for assessment of eligibility.
8. Blood will be tested for HBsAg, anti-HAV IgM, anti-HCV Ab, and anti-HIV Ab.

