## **9.9 Duration of the Study**

For an individual subject, the maximum duration of the study for each subject will be:

- Part A (SAD): up to 42 days (including up to 28 days for Screening, up to 7 days treatment and up to 7 days Follow-up).

- Part B (MAD): up to 42 days (including up to 28 days for Screening, up to 8 days treatment and up to 6 days Follow-up).

The study will close when all subjects have completed the Final Follow-up Visit.

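### SAEs are reportable for 30 days after the last dose whatever the cause, but no contact is scheduled after Day 14, so 17 of the 30 days in Part A and 23 of 30 in Part B depend on spontaneous reports

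*Protocol*

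**What the plan says.** Four parts of the protocol bear on how long SAEs are sought and reported.

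- **Section 6.4.1.5** sets a window counted from the last dose. Besides SAEs arising during observation, it covers "all SAEs occurring up to 30 days after receiving the last dose of study drug, whether considered to be associated with the study drug"; unrelated events are therefore included. It then adds a second rule, under which only events judged drug-related count: "SAEs occurring after the end of the study should be reported to the Sponsor/PAREXEL by the Investigator if the Investigator considers there is a causal" …
- **Section 6.4.1.4** sets a different end point for AEs in general: "AE reporting will extend from signing of informed consent until completion of Follow-up Visit". Section 6.4.1.1 places serious and non-serious events under the same collection duty. After the end of the study, section 6.4.1.4 also asks only for events judged causal.
- **Section 3.1 and Tables 7-1 and 7-2** put the last visit at Day 14 (±1 day) in both parts. For Part B: "Subjects are required to return for a Follow-up Visit on Day 14". Neither table has a later visit, call or other contact.
- **Section 9.9** limits each subject to 42 days and defines closure for the study as a whole: "The study will close when all subjects have completed the Final Follow-up Visit".

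**The concern.** Safety and tolerability are the primary objective of this first-in-human trial (section 2.1). The protocol sets a 30-day, all-causality SAE window, but its schedule stops well inside that window. After Day 14 a discharged healthy volunteer is not asked anything, and the documents contain no instruction to subjects to report an SAE after that visit. For that stretch, the absence of a report is weaker evidence than the absence of an event. The gap is longer after repeated dosing than after a single dose.

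The text also gives the site more than one stopping rule: the Follow-up Visit (6.4.1.4), 30 days after the last dose (6.4.1.5), and a causal-only rule after the end of the study (both sections).

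**Working it through.** **Inputs**

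- SAE window: 30 days after the last dose (section 6.4.1.5).
- Last dose: Day 1 in Part A (Table 7-1); Day 7 in Part B, once daily for 7 days (section 3.1, Table 7-2).
- Last scheduled contact: Day 14, allowed range Day 13 to 15 (Tables 7-1 and 7-2).
- Planned subjects: 40 + 8 = 48 in Part A and 32 + 8 = 40 in Part B (section 4.4).

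**The plan's own figure.** Section 9.9 gives 42 days per subject: 28 + 7 + 7 = 42 in Part A and 28 + 8 + 6 = 42 in Part B. Both reproduce. After up to 28 days of screening, both end at Day 14.

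**Days without scheduled contact**

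Window end = last-dose day + 30. Days covered = follow-up day − last-dose day. Days uncovered = 30 − days covered.

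| | Part A | Part B |
|---|---|---|
| Window ends | 1 + 30 = Day 31 | 7 + 30 = Day 37 |
| Covered, visit on Day 14 | 14 − 1 = 13 | 14 − 7 = 7 |
| Uncovered | 30 − 13 = 17 (56.7%) | 30 − 7 = 23 (76.7%) |
| Visit on Day 15 | 16 (53.3%) | 22 (73.3%) |
| Visit on Day 13 | 18 (60.0%) | 24 (80.0%) |

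Weighted by planned numbers, the uncovered share is (48 × 17 + 40 × 23) / (88 × 30) = 1,736 / 2,640 = 65.8%. The pooled figure describes neither part, so the two should be quoted separately.

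**The two rules in section 6.4.1.5.** Take an unrelated SAE on Day 20.

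- If the end of the study means closure as in section 9.9, a subject in an early cohort is still inside an open study on Day 20. The 30-day rule applies and the causal-only rule does not. The two rules collide only for subjects whose 30 days run past closure. If that is one Part B cohort of 8, the overlap is at most 8 × 23 = 184 of 2,640 subject-days (7.0%).
- If the end of the study means the subject's own last visit, the two rules collide for everyone from Day 14 to Day 31 or 37.

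On either reading, the cut-off at the Follow-up Visit in section 6.4.1.4 does not match the 30 days in section 6.4.1.5.

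**The SAP.** Section 6.3.4 imputes a completely unknown AE end date as the date of final follow-up. An SAE that began on Day 20 with no end date would then end before it started. The SAP rules do not provide for events after the visit.

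**The case against.** The strongest reply is that section 6.4.1.5 creates a reporting duty and not an assessment schedule. It names the observation period and the 30 days separately, so its authors evidently expected the window to outlast observation. Section 6.4.1.1 accepts spontaneous, unsolicited reports, section 6.4.1.6 follows known events to resolution, and an SAE that the site learns of on Day 20 is reportable within 24 hours. This stands. A reader might infer that the later days are never assessed, but the documents do not support that. What is missing is active, scheduled ascertainment.

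Sections 6.4.1.4 and 6.4.1.5 can also be read as a general rule and a specific one, with the specific rule governing SAEs. That is a fair reading, but the text does not state it, and it leaves the schedule unchanged.

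A reader might further infer that the report would present SAE counts under a 30-day rule. It would not, on the present plan. SAP section 6.3.15.1 lists and summarizes SAEs, defines treatment-emergent events without a 30-day limit, and plans no 30-day rate or denominator.

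Finally, on the predicted half-life of 9.27 hours (section 5.3), Day 14 is 7 × 24 / 9.27 ≈ 18 half-lives after the last dose in Part B and 13 × 24 / 9.27 ≈ 34 in Part A. That weakens the case for a large effect. But the figure was predicted before any human data, and the protocol chose 30 days with that prediction in hand.

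**Conclusion.** The point holds as a gap between the stated SAE window and the schedule, together with wording that needs reconciling. Days that rely on spontaneous reports alone are 17 of 30 (57%; 53% to 60% over the visit window) in Part A and 23 of 30 (77%; 73% to 80%) in Part B. The figures assume all planned doses and a Follow-up Visit within its window. Subjects who stop early have an Early Discontinuation Visit as soon as possible (section 7.2.4), and the uncovered stretch can be longer for them.

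A reader might take the contradiction within section 6.4.1.5 as trial-wide. With closure as defined in section 9.9 it reaches essentially the last cohort, assuming that earlier cohorts' 30 days have ended by then. No endpoint, sample size or planned analysis depends on the 30 days. This is an inexpensive improvement to safety ascertainment and does not threaten the trial's conclusions.

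**What to change.** - Add one scripted telephone SAE check 30 days after the last dose to Tables 7-1 and 7-2, recorded in the eCRF, with a window that does not open before day 30.
- State in section 6.4.1.4 that SAEs follow the 30-day window of section 6.4.1.5.
- In section 6.4.1.5, start the causal-only rule after that window and not at an undefined end of study.
- Align section 9.9, both individual duration and closure, and let final follow-up in SAP section 6.3.4 mean the call where SAE dates are imputed.

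**Cost.** At most 88 short calls for the planned subjects (48 + 40), plus any replacements. Participation would run to about Day 31 or Day 37, so the 42-day maximum becomes about 28 + 31 = 59 days in Part A and 28 + 37 = 65 in Part B. Close-out for the last cohort could move by up to about 37 − 14 = 23 days. A protocol amendment is needed, with approval as section 9.8 requires and possibly a revised consent form (section 9.7).

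Shortening the all-causality window to the Follow-up Visit would also make the text consistent and needs only wording. It does so by giving up safety reporting that the protocol now requires, so it is not the change recommended here.

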**PAREXEL International**  
**Toll free SAE [contact]-hour service)**  
**SAE [contact]**  
**Email: [Medical\\[contact]](mailto:[contact])**

#### *6.4.1.6 Follow-up of Adverse Events*

All AEs experienced by a subject, irrespective of the suspected causality, will be monitored until the AE has resolved, any abnormal laboratory values have returned to baseline or stabilized at a level acceptable to the PI, until there is a satisfactory explanation for the changes observed, until the subject is lost to follow-up, or until the subject has died.

#### *6.4.1.7 Suspected Unexpected Serious Adverse Reactions*

Any AE that is serious, associated with the use of the study drug, and unexpected (SUSAR) has additional reporting requirements, as described below.

- If the SUSAR is fatal or life-threatening, associated with the use of the study drug, and unexpected, Regulatory Authorities and IECs/IRBs will be notified within 7 calendar days after the Sponsor learns of the event. Additional follow-up (cause of death, autopsy report, and hospital report) information should be reported within an additional 8 days (15 days total).
- If the SUSAR is not fatal or life-threatening but is otherwise serious, associated with the use of the study drug, and unexpected, Regulatory Authorities and IECs/IRBs will be notified within 15 calendar days after the Sponsor learns of the event.

The Sponsor will notify the Investigators in a timely fashion of relevant information about SUSARs that could adversely affect the safety of subjects. Follow-up information may be submitted if necessary.

The Sponsor will also provide annual safety updates to the Regulatory Authorities and IECs/IRBs responsible for the study. These updates will include information on SUSARs and other relevant safety findings.

#### *6.4.1.8 Pregnancy*

If a female partner of a male study subject who has been exposed to the study drug becomes pregnant, the pregnancy and outcome of pregnancy should be monitored.

Pregnancy alone is not regarded as an AE unless there is a suspicion that the study drug may have interfered with the effectiveness of a contraceptive medication.

All pregnancies in female partners of male subjects must be reported by the Investigator to PAREXEL/Sponsor on the initial pregnancy report form within 30 days after becoming aware of the pregnancy. The Investigator must follow-up and document the course and the outcome of all pregnancies even if the study has finished.

All outcomes of pregnancy must be reported by the Investigator to PAREXEL/Sponsor on the pregnancy outcome report form within 30 days after he or she has gained knowledge of the normal delivery or elective abortion.

#### **6.4.2 Laboratory Variables**

Laboratory assessments will be performed locally at study center's laboratory by means of their established and validated methods. Before starting the study, the Investigator will supply PAREXEL/Kainos with a list of the normal ranges and units of measurement.

The Investigator may decide to repeat the tests, should the results be outside normal ranges and considered clinically relevant, or if the original sample could not be analyzed.

The following laboratory variables will be determined in accordance with the Schedule of Procedures (Table 7-1 and Table 7-2):

**Table 6-2: Laboratory Assessments**

Test Group	Analyte/Component	Test Group	Analyte/Component
Hematology:	erythrocytes mean corpuscular volume (MCV) mean corpuscular hemoglobin (MCH) neutrophils eosinophils basophils lymphocytes monocytes platelets leukocytes hemoglobin hematocrit	Urinalysis:	pH protein glucose ketone bilirubin blood nitrite
Clinical chemistry:	albumin creatinine glucose urea uric acid total bilirubin (TBIL) direct bilirubin total protein triglycerides (TG) total cholesterol low-density lipoprotein (LDL) cholesterol high-density lipoprotein (HDL) cholesterol	Liver enzymes:	alkaline phosphatase (ALP) aspartate aminotransferase (AST) alanine aminotransferase (ALT) gamma-glutamyl transpeptidase (GGT)
Electrolytes:	sodium potassium calcium chloride	Serological marker:	Hepatitis B surface antigen (HbsAg) Anti-Hepatitis A Virus Immunoglobulin M (HAV IgM) Anti-Hepatitis C Virus (HCV Ab) Anti-Human immunodeficiency virus (HIV Ab)

Test Group	Analyte/Component	Test Group	Analyte/Component
Urine drug and cotinine screening, alcohol breath test	Amphetamines Barbiturates Benzodiazepines Cannabinoids Cocaine Opiates Cotinine Alcohol		

Clinical significance of out-of-range laboratory findings is to be determined and documented by the Investigator/sub-Investigator who is a qualified physician. Clinically relevant changes will be recorded as AEs in the eCRF (see Section 6.4.1.2).

For safety laboratory tests, the total volume of blood drawn will be approximately 51 mL for subject in Part A SAD and approximately 51 mL for subject in Part B MAD. Additional safety samples may be collected if clinically indicated at the discretion of the Investigator.

#### 6.4.3 Vital Signs

The following vital signs will be assessed in accordance with the Schedule of Procedures (Table 7-1 and Table 7-2):

- BP, supine (systolic and diastolic; mmHg)
- Pulse, supine (beats per minute)
- Body temperature (°C) (tympanic)

BP and pulse will be measured using the normal practice at study center; after the subject has been in a supine position for at least 5 minutes.

If the subject experiences any changes during the visits which fulfill the criteria of an AE it must be recorded as such (see Section 6.4.1).

#### 6.4.4 Electrocardiograms

Standard 12-lead ECGs will be performed in accordance with the Schedule of Procedures (Table 7-1 and Table 7-2).

ECG will be performed using an internationally recognized 12-lead cardiograph (10 sec. rhythm strip) after the subject has been resting in a supine position for 5 minutes. All records will be done in triplicate within 5 minutes, with at least a 1-minute interval. ECG printouts will include: date, time, at least 2-3 complexes for 12 leads data, HR, QRS duration, P-R interval, R-R interval, QT interval, and QTcF (QT interval corrected for HR according to Fridericia).

- $QTcF = QT \times R-R^{1/3}$

ECG recording will be performed according to the relevant site SOP. The review of the ECG must be done by the Investigator or delegate. The interpretation of the ECG result must follow the categories: “normal”, “abnormal, not clinically significant”, or “abnormal, clinically significant”. Clinically significant findings must be recorded as AEs, or if present at Screening, it should be documented as concomitant illness (see Section 6.4.1).

#### **6.4.5 Physical Examinations**

Physical examinations will be performed in accordance with the Schedule of Procedures (Table 7-1 and Table 7-2).

The examinations will include:

- General appearance
- Head, ears, eyes, nose, throat, neck
- Lymph node palpation
- Abdomen
- Skin
- Extremities
- Respiratory system
- Cardiovascular system
- Gastrointestinal system
- Musculoskeletal system
- Central and peripheral nervous system

If the subject experiences any changes during the visits which fulfill the criteria of an AE it must be recorded as such (see Section 6.4.1).

### **6.5 Demographics and Baseline Characteristics**

Demographics and baseline characteristics will be assessed at Screening (Visit 1).

#### **6.5.1 Subject Demography**

The following demography information will be collected at Visit 1:

- age
- sex
- race

#### **6.5.2 Body Measurements**

The following body measurements will be performed at Visit 1:

- Body weight (kg)
- Height (cm)
- BMI

#### **6.5.3 Medical History**

Thorough medical examination will be performed by interview and checking medical chart history at Screening (Visit 1); the medical and medication history of subjects should be investigated and recorded in detail.

The medical history will be obtained by interviewing the subject or by inspecting his/her medical records.

For coding of medical history, see Section 9.4.

#### ***6.5.4 Previous and Concomitant Medications***

Previous and concomitant medication will be documented as described in Section [5.8](#).

## 7 STUDY CONDUCT

### 7.1 Schedule of Procedures

**Table 7-1: Schedule of Assessments for Part A (SAD)**

Assessments	Screening Period (V1)	Confinement Days (V2)				Outpatient Visit Day (V3-V4)		Follow-up Visit (V5)
	Day -28 to Day -2	-1	1 	2	3 	Day 4	Day 7	Day 14 (±1 day)
Informed Consent	X							
Randomization and Study Drug Administration 			X					
Inclusion/Exclusion Criteria	X	X 						
Demography	X							
Medical/Medication History	X							
Assessment of AEs	X	X	X	X	X	X	X	X
Concomitant Medications	X	X	X	X	X	X	X	X
Vital Signs 	X	X	X	X	X	X	X	X
12-lead ECG 	X	X	X	X			X	X
Physical Examination	X	X			X	X	X	X
Height, Weight, BMI 	X							
Serology 	X							
Drug/Alcohol/Cotinine Screen	X	X						
Safety laboratory: Hematology, Serum Chemistry, Urinalysis 	X	X		X			X	X
Blood Pharmacokinetic Sampling 			X	X	X	X		
Urine Sampling 				X	X			
Scales 			X	X	X	X		
C-SSRS 	X				X			

AE: adverse event; BMI: body mass index; BP: blood pressure; C-SSRS: Columbia Suicide Severity Rating Scale; K-WAIS-IV: Korean Wechsler Adult Intelligence Scale-IV; ECG: electrocardiogram;

ED: Early Discontinuation; HCV: hepatitis C virus; HBsAg: hepatitis B surface antigen; HAV: hepatitis A virus; HIV: human immunodeficiency virus; VAS: Visual Analogue Scale; POMS: Profile of Mood States

1. On Day 1, any predose procedures should be performed within 2 hour before study drug administration.
2. Discharge assessments to be performed for ED are the Day 3 assessments supplemented with an ECG and safety labs, see Section 7.2.4.
3. Randomization occurs on Day 1 prior to dosing.
4. Confirmation of inclusion and exclusion criteria.
5. Vital signs include tympanic temperature, supine pulse and supine BP. Vital signs will be collected after the subject has been in a supine position for at least 5 minutes. On Day 1, vital signs will be measured at predose, and at 0.5, 1, 2, and 4 hour postdose.
6. 12-lead ECGs will be obtained in triplicate within 5 minutes, with at least a 1-minute interval. On Day 1, ECGs will be recorded at predose and at 1 hour postdose. ECGs should be performed prior to pharmacokinetic and safety laboratory blood draws.
7. Screening height and weight will be used for BMI calculation for assessment of eligibility.
8. Blood will be tested for HBsAg, anti-HAV IgM, anti-HCV Ab, and anti-HIV Ab.
9. All hematology and serum chemistry labs will be taken after fasting for a minimum of 8 hours.
10. Plasma samples for pharmacokinetics of KM-819 will be obtained on Day 1 predose (within 30 minutes prior

---

to study drug administration) and 0.25, 0.5, 1, 2, 4, 6, 8, 12, 24, 48, and 72 hours postdose.

11. Urine samples will be taken at: Day 1 predose (within 1 hour before study drug administration) and from 0 to 24 hours postdose.
12. Bond and Lader VAS, POMS, and K-WAIS-IV will be performed on Day -1, Day 1 (predose) and at 3, 6, 12, 24, 48, and 72 hours postdose ( $\pm$  30 minutes for each time point).
13. The version of the C-SSRS to be performed at Screening is the “Baseline-Screening for Phase 1,” and the version of the C-SSRS to be performed on Day 3 (or at ED) is the “Since Last Visit”.

